2. Qualitative key informant interviews will be conducted by study coordinator with key providers (1-3 at each site), and administrator (1-2 at each site), and the CHWs (1 at each site). At baseline, the interviews will be incorporated into the workflow analysis to assess current satisfaction and EHR usage and health coaching. At follow-up, the interviews will assess barriers and facilitators to the implementation and adoption process of the integrated EHR-CHW intervention, intervention fidelity, and to solicit recommendations for the replication and scalability of the intervention to other clinical sites.
3. Ethnographic data will be collected by CHWs in Year 1 and by the study coordinator in Year 5 and will be guided by the 5 key steps in a rapid assessment process.

Impact: The proposed study will inform efforts to prevent stomach cancer and reduce the burden of stomach cancer in Chinese American communities served in safety net health systems and establish a reproducible, sustainable patient-centered cancer prevention model integrated within health care systems serving vulnerable communities.

Substudy: The proposed substudy aims to evaluate the feasibility and response rate for the collection of biosamples among Chinese Americans with a clinically confirmed diagnosis of *H. pylori*. The biosamples will be used to assess differences in oral and gut microbiome profiles before and after *H. pylori* antibiotic therapy. This will be achieved through the optional collection of oral and/or fecal biosamples from participants in EHR-CHW Intervention component of the study ‘Patient-Centered Stomach Cancer Prevention in Chinese Americans’. The proposed substudy will inform efforts to develop novel

biomarkers to improve stomach cancer prevention, risk assessment and early detection among Chinese Americans.

B. Background

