B4. Chinese Americans, socio-cultural barriers and lifestyle-related stomach cancer risk factors. *Health care access.* For Chinese American communities, the risk of stomach cancer is compounded by difficulties in accessing healthcare services, and attendant linguistic, cultural, economic and social barriers, which contribute to delayed cancer screenings,²¹⁻²⁴ poor medication adherence, and poor disease self-management skills.²⁵⁻²⁸ *Acculturation* (which includes indicators such as nativity, years in the US, English language proficiency) is a significant factor that influences health access and behaviors for Chinese American immigrant communities, including impacting screening and disease prevention.^{25,26}

B5. Evidence-base for test-and-treat in high-risk Chinese populations.

The American College of Gastroenterology's 2017 clinical guidelines for treating *H. pylori* infection recommends clarithromycin triple therapy consisting of a proton pump inhibitor (PPI), clarithromycin, and amoxicillin or metronidazole for 14 days where *H. pylori* clarithromycin resistance is known to be <15%.²⁹ This is an oral regimen of 6-8 pills taken daily at different dosing intervals for 14 days. Test for treatment success of eradication therapy should occur at least 4 weeks after completion of antibiotics and with patients off PPI for 1-2 weeks, using urea breath test, fecal antigen test, endoscopic testing or other clinically approved *H. pylori* infection diagnostic test.

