Substudy Design. The substudy is an observational feasibility pilot study. We aim to enroll a minimum of 10 participants. Only participants already enrolled in the main study are eligible for the substudy (see *Section II*). After enrollment into the main study, trained study staff will introduce study subjects to the substudy and offer subjects the opportunity to participate in the substudy in several ways: 1) provision of oral wash sample only; 2) provision of stool sample only; and 3) provision of both oral wash and stool samples. Study staff will obtain verbal informed consent from interested individuals (See *Combined Verbal Informed Consent*). Study staff who have obtained the verbal consent will document the consent and the date of consent on the Enrolled Participants Log. The Enrolled Participants Log is the only record linking a participant's name, subject ID and substudy ID (if applicable). Substudy participants will have the option of mail or in-person pick-up for receiving study materials, which include the kits to collect oral wash and fecal samples, participant instructions (See *Substudy Instruction Booklet*), and return stamped envelope. Once the substudy materials are received, study staff will set up an appointment to call or meet with substudy subjects remotely via WebEx and answer any questions about sample collection and returning the samples of the participant's choice.

After the completion of their *H. pylori* antibiotic therapy (approximately two months after enrollment), subjects will be sent or given another biosample collection kit with instructions and a return stamped envelope for sample collection. For those who did not return study samples, study staff will give a reminder call by phone and/or text message (See *Script for Substudy Telephone Text Reminders*). Subjects who return incomplete or unusable study samples will be sent or given another biosample collection kit with instructions and return stamped envelope.

II. CHARACTERISTICS OF THE RESEARCH POPULATION

The overall number of subjects expected to participate in the EHR-CHW Intervention study is 144. Key

informant interviews will be conducted with approximately 10-12 individuals (project CHWs, providers, and administrators).

EHR-CHW Intervention

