 - b. Just before finishing a bowel movement, use a piece of toilet paper to collect a small sample of stool.
- 3) Use spoon attached to cap to collect 2 marble sized samples.
- 4) Carefully screw the cap closed with sample on spoon. Shake well.
- 5) Once the collection is complete, place the tube in the preaddressed package and seal carefully. Return to the study center by mail within one day of collection.

Oral wash biosample collection: Study participants will be asked to swish vigorously with one aliquot of 10 ml Scope Original mouthwash sample (*Proctor & Gamble, Cincinnati, OH*) for 30 seconds.

Participants will be directed to expectorate the mouthwash into a clean specimen tube, and return to the study center by mail within one day of collection.

B. Data Analysis and Data Monitoring

B1. EHR-CHW Intervention Analysis.

We will conduct analyses to determine the comparability of the participants in the 2-arms using standard techniques, including Student's t-tests for normally distributed variables (after necessary transformations) and chi-squared tests for dichotomous variables. If the randomized groups differ in baseline characteristics, we will adjust for those variables in subsequent analyses of program effects. Descriptive statistics will be calculated to characterize study participants and to evaluate the distribution of key clinical, sociodemographic, and outcome variables. Summary data on medical history, years in the US, access to and utilization of primary health care services, and social characteristics (e.g., marital status, employment) will be reported.

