To safeguard confidentiality and anonymity, unique identifiers will be assigned to all participants for all portions of the study and all data collection instruments will identify participants only by these unique identifiers. On the baseline and follow-up surveys, the first page of the survey will ask participants for updated contact information so that study staff can maintain contact throughout the intervention period. After the data is collected, the first page of the survey will be removed from the remainder of the survey instrument (which will only contain unique identifiers). Data will be entered into REDCap, a survey database platform, by a study staff member. Only study staff will have password protected access to the data. [name] will serve as the data manager for this study. The Data Manager will be responsible for the management of information obtained at the various clinic sites.

The database will be stored on REDCap's secure database system, which will be utilized for data management purposes. Survey pages containing participant names and contact information and logs linking subjects' identifying information to study numbers will be kept locked in a file cabinet in a secure location. Paper baseline and follow-up survey data will be kept separate from identifiable information and kept in locked file cabinets in a secure location. Contact information from consented participants will be kept on file for the duration of the trial and will be destroyed (both electronic and hard copy) upon the dissemination of trial results (approximately 5 years).

Substudy Biosample Handling and Security. The samples in containers will be received by mail via USPS at NYU Smilow Research Center and stored at -80 °C at a laboratory facility with space dedicated to our study samples. Within two weeks of receipt, DNA will be isolated from these specimens and used to conduct microbiome assays. Vials will only be labeled with unique study numbers and be clearly marked as substudy samples. No samples will be collected in a vial labeled with patient identifiers. If a sample does arrive with patient identifiers, those identifiers will be removed and discarded by study staff before storage and will be replaced with a unique study number. Samples will be stored for the duration of the study and destroyed upon the dissemination of trial results (approximately 5 years).

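### The two-week DNA extraction rule puts essentially every before/after pair of substudy samples on different extraction dates, and the plan neither records nor adjusts for batch

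*Combined protocol and SAP*

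**What the plan says.** The Substudy paragraph of the opening summary and section B9 (Substudy Background) both say what the samples are for: to "assess differences in oral and gut microbiome profiles before and after" antibiotic therapy. Section C4 (Substudy Design) describes an observational feasibility pilot with at least 10 participants and sets the timing of the second sample: after "antibiotic therapy (approximately two months after enrollment), subjects will be sent or given another biosample collection kit with instructions".

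The laboratory rule is in section III.C, Substudy Biosample Handling and Security. Samples arrive by post, are kept at -80 °C, and then: "Within two weeks of receipt, DNA will be isolated from these specimens and used to conduct microbiome assays". No exception is made for a sample whose pair has yet to arrive. The same paragraph adds: "Samples will be stored for the duration of the study".

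Section III.B1a (Substudy Data Analysis) covers 16S sequencing, clustering, diversity measures, principal components and relative abundance. It mentions no batch term, extraction control or run layout. Under Substudy Data Handling and Security, the database tracks what each sample is, where it is kept, when it was collected and stored, and its study number. Extraction date, extraction batch and sequencing run are not among the fields.

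**The concern.** A before/after comparison within one person is useful because whatever is common to both samples cancels. Laboratory batch cancels only if both samples go through the same run. A deadline that runs separately from each sample's receipt, with samples about two months apart, prevents that. Each observed change is then the true change plus a difference between two extraction batches.

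At stake is the exploratory microbiome comparison, which the protocol offers as groundwork for biomarkers. With perhaps 10 pairs there is little room for avoidable noise. Because the after sample is always processed later, a laboratory trend could also be taken for an effect of antibiotics.

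**Working it through.** The plan gives no power or sample-size figure for the microbiome comparison, so there is none to reproduce.

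**1. Can a pair share an extraction run?**

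Inputs: extraction at most 14 days after receipt (section III.C); second kit about day 60 after enrollment (section C4); mailing: "Return to the study center by mail within one day of collection" (section III.A2); length of therapy from the background in section B5: "This is an oral regimen of 6-8 pills taken daily at different dosing intervals for 14 days". The protocol itself does not fix the regimen.

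A sample received on day r can be extracted from day r to day r + 14. Two windows overlap only if r2 − r1 ≤ 14. Otherwise they are (r2 − r1) − 14 days apart:

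| Days between receipts | Days between windows |
|---|---|
| 14 | 0 (they touch) |
| 21 | 7 |
| 28 | 14 |
| 45 | 31 |
| 60 | 46 |

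If the second kit goes out on day 60 and its sample arrives L days later, the first sample must arrive on day 46 + L or later to share a run: day 46, 53 or 60 for L = 0, 7 or 14. With a 14-day course between a true before sample and the after sample, plus kit dispatch and post, the gap exceeds 14 days even then.

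**2. Noise, if each visit is its own batch**

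Table 4 gives the substudy six quarters: 18 × 30.4 / 14 = 39 two-week windows. Ten participants make 20 sampling visits, 20 / 39 = 0.51 per window. If enrollment is spread out, most visits stand alone.

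Let σ be the per-sample residual SD and kσ the between-batch SD (k is assumed; the documents give no value). The variance of a within-person change is 2σ² in a shared batch and 2σ²(1 + k²) in separate batches. Ten pairs are then worth 10 / (1 + k²). Illustrative test: paired t, 10 pairs, two-sided 5%, 9 df, critical value 2.262, a true change of 1 SD of the batch-free within-person change, noncentrality √10 / √(1 + k²).

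| k | Variance factor | Pairs' worth | Power |
|---|---|---|---|
| 0 | 1.00 | 10.0 | 80.3% |
| 0.1 | 1.01 | 9.9 | 79.9% |
| 0.2 | 1.04 | 9.6 | 78.8% |
| 0.3 | 1.09 | 9.2 | 76.9% |
| 0.5 | 1.25 | 8.0 | 71.2% |
| 1.0 | 2.00 | 5.0 | 51.4% |

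**3. Clustered enrollment**

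The batch contribution to the mean change over 10 pairs has SD √(2/10) = 0.45 batch SDs if all 20 visits are separate batches. It is √2 = 1.41 if all before samples share one run and all after samples another. A simulation with assumed inputs (runs every 14 days, return lags of 3 to 21 days, second kit at day 60) gave:

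| Enrollment spread | SD of batch contribution (batch SDs) | Runs holding both time points |
|---|---|---|
| all together | 1.11 | 0% |
| 30 days | 0.91 | 0% |
| 60 days | 0.74 | 6% |
| 90 days | 0.60 | 18% |
| 180 days | 0.49 | 22% |
| 540 days | 0.45 | 11% |

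No pair shared a run in any setting.

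**4. Drift**

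Let δ be the systematic later-minus-earlier difference, in SDs of the within-person change (assumed). With no true change, the same test has noncentrality δ√10. For δ = 0.1, 0.3 and 0.5 this is 0.32, 0.95 and 1.58, and the false-positive rates are 5.9%, 13.6% and 29.3%.

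**The case against.** The strongest reply is about weight. The substudy's stated aim is whether samples can be collected and how many people return them, and the extraction date does not touch that. The analysis section plans descriptive output and names no test, alpha or effect size, so the power and error rates above belong to a test supplied for illustration. The documents do not exclude a negligible batch effect: at k = 0.1 almost nothing is lost. The upper drift values are also demanding. A steady 0.3 to 0.5 SD per two months would add up to 2.7 to 4.5 SD over 18 months (nine two-month steps). All of this stands, and it limits the priority.

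Four stronger readings are tempting, but the documents do not support them:

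- **A pair can never share a batch.** The two months run from enrollment to issue of the second kit, and the first sample has no return deadline. A very late first sample could qualify, though with a 14-day course it would hardly be a before sample.
- **Batch is fully confounded with time point.** Under staggered enrollment some runs mix one person's before sample with another's after sample, and the effect is mainly noise. It acts as bias if enrollment is clustered or conditions drift.
- **The split cannot be repaired.** Samples are kept for the whole study, so leftover material might be re-extracted in pairs. The protocol does not clearly date sequencing, so stored DNA might be sequenced in one run, though that leaves extraction split. Different dates need not mean different reagent lots. These are possible rescues that the plan does not call for.
- **The -80 °C storage shows that the two-week limit serves no purpose.** Prompt extraction reveals failed DNA yield early, which helps the rule in section C4 of sending a new kit for unusable samples.

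It may also be said that run layout is laboratory detail that a pilot protocol can omit. That does not answer the point. The protocol states a rule, and following it separates the pairs.

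**Conclusion.** The concern holds for the exploratory before/after comparison only. On the planned schedule essentially every pair is extracted on different dates, and nothing in the analysis or tracking plan adjusts for batch or records it. Comparing relative rather than absolute abundance deals with differing read counts, not with batch differences in composition.

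The timing result rests on the protocol's own intervals and the 14-day course in its background. The size cannot be settled from the documents. It runs from negligible to a loss of half the information in 10 pairs over the assumed range of batch SD, and from a 6% to a 29% false-positive rate over the assumed range of drift. Feasibility, response rate and the trial's primary outcome, *H. pylori* eradication, are untouched. This is a cheap improvement of low to moderate priority.

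**What to change.** Replace the two-week sentence in Substudy Biosample Handling and Security with wording such as: *Samples will be held at -80 °C. Each participant's before and after samples will be extracted in the same batch and sequenced in the same run, in random order, once the second sample has been received or the substudy closes.* Add extraction batch and sequencing run to the database fields under Substudy Data Handling and Security. The batch term then cancels within each pair.

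The cost is one replaced sentence and two database fields, in a freezer already planned. Two downsides should be stated in the protocol:

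- Before samples spend about two months longer frozen than their pairs, which is itself a difference aligned with time point.
- Low DNA yield comes to light later, so the decision at receipt to send a replacement kit would rest on visible volume and integrity only.

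If the laboratory has a reason to keep the two-week limit, the fallback is to record the batch, include extraction controls and adjust for batch. That can correct only part of the problem.

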[name] is the Research Data Manager for the NYU Center for the Study of Asian American Health. She manages and oversees the data sources across CSAAH, which includes the NYU-CUNY PRC, and performs analyses and assists with the dissemination of study findings. In addition, she provides epidemiological and biostatistical support for grant development activities within the center. [name] received her MPH in Epidemiology from Columbia University, Mailman School of Public Health and also studied public health at the University of North Carolina at Chapel Hill.

VI. SUBJECT IDENTIFICATION, RECRUITMENT AND CONSENT/ASSENT

A. Method of Subject Identification and Recruitment

EHR-CHW Intervention: *H. pylori* infected individuals will be identified and recruited into the study from the following NYC health care facilities: NYU Langone Health – which includes NYU Langone Brooklyn, NYU Langone Brooklyn Family Health Centers and affiliated provider practices, and NYU Ambulatory Care Centers – Bellevue Hospital Center and Gouverneur Hospital. Participants will be identified by 2 approaches: 1) using ICD codes for *H. pylori* and Chinese ethnicity identified through a race and language code available in EHR, patients with recently diagnosed *H. pylori* infection (within 7-days) will be identified; via a EHR registry list, and 2) patients will be recruited directly at the above mentioned sites, all of which serve a substantial Chinese American population. In endoscopy clinics, patients are routinely evaluated for *H. pylori* infection.

CHWs will complete a brief screening form with potential participants in person or via phone, depending on the preference of the potential participant and the safety of the study staff and potential participants. The form will assess demographic characteristics, participant eligibility, COVID-19 symptoms, interest in our program, and reasons for refusal to participate. For in-person screenings, if the patient is eligible and interested in the study, the CHW will obtain verbal informed consent for study participation and describe the randomization process (See *Combined Verbal Informed Consent*). All study staff will follow COVID-19 workplace safety, personal protective equipment and social distancing policies at each recruiting clinic site and as required by NYUGSOM.

Individuals identified from the registry list will receive phone calls by CHWs (See *Combined Script for Telephone Screening*), during which CHWs will explain the study and elements of informed consent, and will complete the process for verbal informed consent over the phone with interested, eligible individuals. Participant names and phone numbers will be needed in order for the CHWs to contact participants regarding participation in the intervention (Please see *Application for Waiver of Authorization and Documentation of Consent*). In addition, a screening form (See *Telephone Screening Form for CHW Intervention*) will be completed to verify eligibility. CHWs will call patients a maximum of 3 times over a one-week period at varying times of the day to invite them to enroll in the study. CHWs will compile and share contact information for consented study participants with the study coordinator on a weekly basis.

Substudy. The substudy is only open to participants who are enrolled in the EHR-CHW intervention. Once participants have consented to being in the EHR-CHW intervention, CHWs will explain the substudy and elements of informed consent, and will complete the process for verbal informed consent over the phone with interested individuals. Study staff who have obtained the verbal consent will

document the consent and the date of consent on the Enrolled Participants Log. The Enrolled Participants Log is the only record linking a participant's name, subject ID and substudy ID (if applicable). No undue pressure will be given to subjects to participate in both studies as participation is entirely voluntary (See Combined Verbal Informed Consent).

Key Informant Interviews. Participating providers, administrative staff and community health workers of clinic sites will receive an invitation to participate in the interview (See *Invitation and Elements of Informed Consent for Key Informant Interview*). No undue pressure will be given to subjects for participation as the participation is entirely voluntary (See *Verbal Consent Script for Key Informant Interview*).

B. Process of Consent

All study personnel will have completed the NYU IRB Mandatory Tutorial and IRB Health Insurance Portability and Accountability Act (HIPAA) Training before commencing any data collection activities. The informed consent form for this study have been created by the NYU School of Medicine Office of Science and Research in accordance with Federal guidelines, including HIPAA.

EHR-CHW Intervention. To maintain consistency in consent procedures and to reduce selection bias, verbal informed consent obtained for both in-person and telephone enrollment (see *Application for Waiver of Authorization and Documentation of Consent*).

If screening is conducted in person, consent processes will take place at clinic sites in a manner that maximizes confidentiality and privacy and allows questions to be asked. All study staff will follow COVID-19 workplace safety and personal protective equipment policies at each recruiting clinic site and as required by NYUGSOM. Participants will be screened in advance for symptoms and asked in advance to wear a mask/face covering. All study staff and participants will follow efforts for social distancing whenever possible. Eligible participants demonstrating interest in participating in the project will meet with a study team member who will explain the intervention and answer any questions. Verbal consent (see *Combined Verbal Informed Consent*) will be obtained in a location allowing privacy and appropriate social distancing, on a one-on-one basis.

Participants are free to withdraw from participating in the study at any time without repercussions. Participants will be advised during the consent process that they have the right to withdraw entirely and that their refusal will not jeopardize their relationships with their CHW or primary care physician.

Substudy. Only participants already enrolled in the main study are eligible for the substudy. Study staff will obtain verbal consent from interested participants (see *Combined Verbal Informed Consent*) and offer subjects the opportunity to participate in the substudy in several ways: 1) provision of oral wash sample only; 2) provision of stool sample only; and 3) provision of both oral wash and stool samples. Participants will be advised participation in the substudy is optional and that their refusal to participate in the substudy will not jeopardize their participation in the EHR-CHW Intervention. Participants are free to withdraw from the substudy at any time without repercussions.

Key Informant Interviews. A Waiver of Documentation of Consent is being requested for participants of Key Informant Interviews for this study (See *Application for Waiver of Documentation of Consent for*

Key Informant Interview). This request is being made because the consent form, if collected would require names to be collected and in doing so would be the only record linking the subject's name to the research. Verbal consent will be obtained to audio-record prior to the start of the interview, but we will not collect any personal information or identifiers. Individual names will not be recorded or appear in interview notes. Participants will be free to withdraw from the interview at any time without repercussions. Participants will be provided with an invitation including the elements of the written consent as well as contact information for the study PI. Verbal consent will be obtained from the key informants prior to beginning the interview in-person or over the phone as preferred by participant (See *Verbal Consent Script for Key Informant Interview*).

C. Capacity

We anticipate that all subjects will have the capacity to give informed consent. Language barriers will be minimized by having data collectors who speak Chinese and translated consent scripts for the CHW intervention (to be translated upon approval of the English version).

D. Subject/Representative Comprehension

To determine that the subject or his/her authorized representative understood the information presented, they will be given the opportunity to ask questions before giving consent to participate. They can also choose at that time not to be in the study. The individuals authorized to obtain consent will do so by going over the Verbal Informed Consent script with the potential subject. The individuals will explain the purpose of the study, the procedures, possible risks and anticipated benefits, that it is voluntary, and how to withdraw if they choose to at a later time. Chinese speaking personnel will obtain consent from limited English-speaking individuals using a translated Verbal Informed Consent script. Subjects will also be asked if they are willing to receive key information about the study by text message. If they are, the Key Information Sheet will be texted to them using an NYU-issued, password-protected telephone.

E. Debriefing Procedures

Information will not be withheld from the subjects related to their participation in the study.

F. Consent Scripts

Please refer to the consent scripts: *Combined Verbal Informed Consent Script* and the *Key Information Sheets for CHW Intervention and the substudy*; and *Invitation and Elements of Consent and Verbal Consent Script* documents for the Key Informant Interview.

G. Documentation of Consent

EHR-CHW Intervention and Substudy. Study staff will obtain consent by reading the verbal informed consent script to the subject or the subject's legally authorized representative, and the subject or representative will be given adequate opportunity to ask questions before verbally consenting. The subject will receive a copy of the key information sheet by text message if they choose so. A translated verbal informed consent and key information sheet will be used for non-English speaking subjects, depending on their preferred language.

Study staff who have obtained the verbal consent will document the consent and the date of consent on the Enrolled Participants Log. The Enrolled Participants Log is the only record linking a participant's name, subject ID and substudy ID (if applicable).

Signed informed consent forms from participants consented in earlier versions of the protocol will be stored in a separate folder in a locked cabinet accessible only to study staff.

Key Informant Interviews. A Waiver of Documentation of Consent is being requested for participants of the Key Informant Interview for this study (see *Application for Waiver of Documentation of Consent for Key Informant Interview*). This request is being made because the consent form, if collected, would require names to be collected and in doing so would be the only record linking the subjects name to the research. Verbal consent will be obtained prior to the start of the interview, but we will not collect any personal information or identifiers. Names of individuals will not be recorded nor appear in interview notes. Participants will be free to withdraw from the interview at any time without repercussions. Participants will be provided with an invitation including the elements of written consent as well as contact information for the study PI. Verbal consent will be obtained from the key informants prior to beginning the interview (See *Verbal Consent Script for Key Informant Interview*).

H. Costs to the Subject

There are no costs to participate in this study. Any doctor visits and laboratory tests, including the fecal antigen test or other clinically approved *H. pylori* infection diagnostic test, are part of standard care.

I. Payment for Participation

Participants will receive a payment of \$25 each time they complete a questionnaire (baseline, 2 months and 6 months). Participants may receive metro cards for travel associated with the project.

Substudy. Subjects will be given a \$20 gift card if they provide one type of sample only (either oral wash or stool), and a \$35 gift card if they provide both oral wash and stool samples. Gift cards will be mailed or given to subjects upon successful return of biosamples collected post-*H. pylori* medication completion.

J. Subject Withdrawal

Any of the participants may withdraw from the study at any time. This will not affect their services and care at the clinic site. If a participant is uncomfortable during an interview or survey administration, the participant may stop at any time without penalty. If a participant withdraws consent, no further data from that participant will be collected.

Early Termination. The study may be suspended or prematurely terminated if there is sufficient reasonable cause. Written notification, documenting the reason for study suspension or termination, will be provided by the suspending or terminating party to the investigator and/or the NIH NIMHD, as applicable. If the study is prematurely terminated or suspended, the PI will promptly inform the Institutional Review Boards (IRBs) and provide the reason(s) for the termination or suspension. Circumstances that may warrant termination include, but are not limited to:

- Determination of an unexpected, significant, or unacceptable risk to subjects.
- Insufficient adherence to protocol requirements.
- Data that are not sufficiently complete and/or evaluable.

VII. FUNDING SOURCE

The main study is supported by NIH-NIMHD U54 MD000538. The substudy is supported by NIH-1P20CA252728-01

VIII. APPENDIX

- A. Combined Script for Telephone Screening
- B. Screening Form for CHW Intervention
- C. Combined Verbal Informed Consent
- D. Key Information Sheet for CHW Intervention
- E. Key Information Sheet for Substudy
- F. Baseline Survey for CHW Intervention
- G. Follow-up Survey for CHW Intervention
- H. Script for Substudy Telephone Text Reminders
- I. Substudy Instruction Booklet
- J. Key Informant Interview Guide
